This study will test an intervention designed to change oral health norms and reduce disparities in oral health among vulnerable adults residing in publicly funded senior housing in Central Connecticut. The intervention model is based on Fishbein's modified theory of reasoned action operationalized through Adapted Motivational Interviewing and Practice-to-Mastery (AMI-PM). The intervention includes two components: 1) a face to face administration of the AMI-PM, a participatory counseling model, and 2) a targeted building-level campaign (CA) consisting of up to three half-day oral health events with skills development through practice to mastery (PM) to parallel the individual intervention (CA+PM), all based on the study's conceptual model. The study uses a modified fractional factorial design to evaluate the face to face and campaign components separately and in different additive sequences. Six buildings will be paired in three dyads. The buildings in each dyad will be randomized to either having the AMI-PM intervention first followed by CA+PM or to having the CA+PM first followed by AMI-PM. Sixty residents will be recruited in each building for a total of 360 participants. There will be four assessments:

- 1) To will include a survey, oral hygiene skills assessment and clinical assessment of the Gingival Index and Plaque Score. The survey will provide data on the conceptual domains that are the target of the tailored intervention;
- 2) T1 will follow the AMI-PM or CA+PM (depending on condition) and will include the survey, oral hygiene skills assessment and clinical assessment of the Gingival Index and Plaque Score. This assessment will occur 1-3 months after the AMI-PM or CA+PM;
- 3) T2 will follow the AMI-PM or CA+PM and will include the survey, oral hygiene skills assessment and clinical assessment of the Gingival Index and Plaque Score. This assessment will occur 1-3 months after the AMI-PM or CA+PM.
- 4) T3 will include oral hygiene skills assessment and clinical assessment of the Gingival Index and Plaque Score. This will

occur 16-18 months after study entry. We will use general linear

occur 16-18 months after study entry. We will use general linear mixed models (GLMM) or general estimating equations (GEE), respectively, to fit a model with intervention and period effects using the MIXED procedure in SAS[®].

Objectives: Primary Objectives:

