12 STATISTICAL CONSIDERATIONS

12.1 Study Hypotheses

- 1. The AMI-PM will produce better short term (T1) clinical outcomes than the Campaign (CA+PM) (AIM 1).
- 2. The CA+PM+AMI-PM will produce better mid-term (T2) and long-term (T3) clinical outcomes than the AMI-PM+CA+PM (AIM 2).
- 3. The AMI-PM will produce more change in mediating cognitive domains than the CA+PM.
- 4. Both AMI-PM+CA+PM and CA+PM+AMI-PM will result in no differences in change in mediating cognitive domains from T0 to T2.
- The greater the dosage (proportion of total talking points recorded for all domains in a tailored AMI; and exposure to campaign activities and messages), the better the outcomes.
- 6. We will investigate an exploratory hypothesis examining the effects of the intervention and sequence on oral health quality of life (a secondary outcome), as well as on clinical outcomes.

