12.2 Sample Size Considerations

Sample size calculations are based on the primary outcomes of continuous measures of the Gingival Index and Plaque Scores using estimates of effect and variation from the pilot grant. The MFFD design has two sequences, called A:B and B:A, and two periods (1 and 2). We will power on the first period, which is essentially a two-arm parallel design with randomization at the building level. The study design will recruit N=60/building, with 3 buildings on sequence A:B (N=180) and three on sequence B:A (N=180).

Table Sample size for a two-group t-test, using a two-sided α =0.05						
Outcome	Source	Mean	Std Dev	Effect	N per	Power
		difference		Size	group	
Plaque Index	Pilot	0.25	0.34 (pilot)	0.74	123	99
Gingival Score	Pilot	0.66	0.60 (pilot)	1.1	123	99
Plaque Index	Pilot	0.25	0.47 (UCL)	0.53	123	98
Gingival Score	Pilot	0.66	0.81 (UCL)	0.82	123	99
Plaque Index	Pilot*.75	0.20	0.47 (UCL)	0.42	123	91
Gingival Score	Pilot*.75	0.50	0.81 (UCL)	0.62	123	99
UCL= Upper 95% CL of the pilot study SD						

Attrition: Longitudinal studies must account for attrition. If we assume a conservative 75% retention rate across the study that would leave us with approximately N=135 per intervention group, or N=45 per building.

Effects of intra-class correlation (ICC) within sites: The cluster design can sometimes impact the power of a study and our calculations consider this human phenomenon. To account for the cluster design, we calculated the effective sample size which is the sample size used for power calculations, according to Killip et al. With this design we expect to have 6 clusters of N=45 each finish the study, or 135 per sequence. Assuming an intracluster correlation coefficient (ICC) of 0.01 or 0.02, which are typical values for human subject studies, this gives effective sample sizes closer to 123. The strategy therefore is to accordingly adjust the sample sizes used in calculations. As a result, our sample size calculations are based on a maximum number of N=123 per intervention (not 135) after accounting for loss of power due to intra-class correlation. Using N=123 per group, our power ranged from 91 to 99 for different scenarios reflecting varied assumptions, as shown in the attached memo from September 5, 2016.

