Intervention variables: As all subjects are exposed to the same interventions, it is of interest to unpack the intervention into 1) dosage (percent of talking points covered for all focal points (domains) addressed in the intervention, and 2) exposure to focal point messages during campaigns. Study Hypothesis #5, regarding dosage of interventions, will be assessed by creating an ordinal scale that measures an individual's exposure to talking points through participation in the AMI and exposure to messages via campaigns, thus creating a measure of dosage. We will then assess if dosage predicts better outcomes. This can be done directly (e.g., compare mean gingival scores across dosage levels with ANOVA) or dosage can be used as a predictor variable in the statistical models and causal pathway analyses. Oral health skills/Practice-to-Mastery (a 4 point Likert scale) and focal points (count variable) can be analyzed using similar techniques and approaches.

MFFD layout: N at the beginning of study			
	Sequence	N	
Building 1	A:B	60	
Building 2	B:A	60	
Building 3	A:B	60	
Building 4	B:A	60	
Building 5	A:B	60	
Building 6	B:A	60	

Secondary Outcome of General Oral Health Assessment Inventory (GOHAI): We will conduct a set of secondary analyses with GOHAI as a continuous outcome. It will also be incorporated into our statistical/mediator models as predictor to see if it acts as an effect modifier.

Cognitive Mediators: The following variables will be incorporated into the causal pathway analysis to address example hypotheses #3 and #4: knowledge, oral health beliefs/norms, social support, oral hygiene behaviors, fears/worries, practice to mastery, and behavioral intentions. We will use longitudinal mediation to compared the efficacy of AMI-PM+CA+PM to CA+PM+AMI-PM in terms of whether they differ significantly in the amount of change that they engender in the gingival index and plaque score, indirectly through the mediators measured in our model.

outcomes.

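### Hypothesis 5 is an ordered claim (more dosage, better outcomes), but the plan fixes no test of order: its one named example, ANOVA, ignores order and direction

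*Combined protocol and SAP*

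**What the plan says.** Section 12.1 lists Hypothesis 5 as a directional statement. Dosage combines the share of talking points covered in the tailored session with campaign exposure, and the claim for it ends: "exposure to campaign activities and messages), the better the outcomes".

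Section 12.4, under intervention variables, proposes "creating an ordinal scale that measures an individual's exposure to talking points through participation in the AMI and exposure to messages via campaigns". The aim is again directional: "We will then assess if dosage predicts better outcomes". Two ways of doing this follow in a single sentence:

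- The first is a direct comparison, with an example introduced by 'e.g.': "compare mean gingival scores across dosage levels with ANOVA".
- The second is the alternative: "or dosage can be used as a predictor variable in the statistical models and causal pathway analyses".

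The plan does not say which route decides Hypothesis 5. It does not say how many levels the scale has, how they are scored, or whether dosage as a predictor would be a class variable or a number. The customised contrasts mentioned elsewhere in Section 12.4 are for comparing time points, not dosage levels. Section 12.2 gives power only for the first-period two-group comparison ("Sample size for a two-group t-test, using a two-sided" alpha of 0.05), so Hypothesis 5 has no stated effect size or power.

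**The concern.** The null hypothesis of an omnibus ANOVA is that all level means are equal, and its alternative is that at least two differ. Relabelling the dosage levels in any order leaves the F statistic unchanged, so the information that the ordinal scale was built to carry is not used. Two things follow:

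- A steady gradient is tested on k−1 degrees of freedom instead of one, which costs power.
- A significant result is compatible with patterns that contradict the hypothesis, such as a benefit only at middle dosage or worse scores at high dosage.

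This would be so even if dosage had been randomised, so it is separate from self-selection into dosage.

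The predictor route removes the problem only if dosage is entered as a score. Entered as a class variable, it gives another unordered test. With the choice left open, two routes that can disagree are both available after the data are seen.

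**Working it through.** **Inputs.**

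- N = 270: 360 enrolled less 25% attrition (Section 4 and Section 12.2).
- Two-sided 0.05: stated in Section 12.2 for the two-group test and assumed here for Hypothesis 5.
- Number of levels k: not stated, so 3 to 6 are shown.
- Total drop d from lowest to highest dosage, in SD units: not stated, so 0.43, 0.6 and 0.8 are shown. The value 0.43 is borrowed from the weakest row of the plan's power table (0.20/0.47 = 0.426). That row is a between-arm plaque difference, not a dosage effect.
- Further assumptions: equal-sized, equally spaced levels and independent persons.

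**The plan's own figure first.** For that weakest row, the noncentrality is 0.426 × √(123/2) = 3.34 on 244 df. Power is 91%, as stated. This confirms the method and says nothing about power for Hypothesis 5.

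**Linear trend.** With equal levels the noncentrality is λ = N·d²·(k+1) / [12(k−1)]. For k = 5 and d = 0.43, λ = 270 × 0.1849 × 6/48 = 6.24. All of λ lies in the linear contrast. The trend test therefore spends it on 1 df, and ANOVA spreads the same λ over k−1 df. Power from the noncentral F, ANOVA against trend:

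| Levels | d = 0.43 | Loss | d = 0.6 | Loss | d = 0.8 | Loss |
|---|---|---|---|---|---|---|
| 3 | 73% v 82% | 9 | 96% v 98% | 2 | >99% v >99% | <1 |
| 4 | 58% v 75% | 17 | 88% v 96% | 8 | 99% v >99% | 1 |
| 5 | 48% v 70% | 22 | 80% v 94% | 14 | 97% v >99% | 2 |
| 6 | 41% v 67% | 26 | 73% v 92% | 19 | 95% v 99% | 4 |

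Losses are in percentage points, taken from unrounded powers.

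**Top dosage no better than the bottom.** Take five equal levels with means 0, −0.4, −0.4, −0.4, 0 (lower is better).

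- ANOVA: the grand mean is −0.24, the between-level variance is 0.6 × 0.4 × 0.4² = 0.0384, and λ = 270 × 0.0384 = 10.37. It rejects about 73% of the time.
- Trend: the linear contrast is zero, so it rejects about 5% of the time.

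**The same pattern with unequal levels (30/25/20/15/10%).**

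- ANOVA: 60% of people are still in the middle levels, so λ is unchanged and so is the 73%.
- Trend: with scores 0 to 4, the mean score is 1.5, the score variance is 1.75 and the covariance with the means is −0.08. Then λ = 270 × 0.08²/1.75 = 0.99, and it rejects about 17% of the time, with an expected slope in the favourable direction.

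**Pure threshold.** Take five equal levels with means 0, −0.4, −0.4, −0.4, −0.4.

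- ANOVA: λ = 270 × 0.2 × 0.8 × 0.4² = 6.91, and power is 53%.
- Trend: λ = 270 × 0.16²/2 = 3.46, and power is 46%.

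**The case against.** The strongest reply is that the plan does not commit to ANOVA. It is an illustration of one of two routes, and the second, dosage as a predictor, is already a trend test if the ordinal scale enters as a score. That stands. A reader might infer that Section 12.4 prescribes an unordered test for Hypothesis 5, but the text does not go that far. What it leaves open is the choice of test.

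The second reply concerns size. A reader might take a loss of 20 to 30 power points as a feature of this plan. The documents do not support that, because they give neither the number of levels nor a dosage effect. At 0.43 SD the loss is below 20 points with 3 or 4 levels, and at 0.6 SD it is below 20 points throughout 3 to 6 levels.

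Third, the trend test is not a complete safeguard. With unequal levels it too can reject for a hump, and it is somewhat weaker for a threshold. Both points are correct and shape the fix.

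Fourth, anyone who looks at the level means would see whether the top dosage beats the bottom, and Hypothesis 5 is neither one of the three objectives in Section 3.1 nor what the study is powered on. This limits the consequences. It does not make the omnibus test answer an ordered hypothesis.

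**Conclusion.** The concern holds in a limited form. Hypothesis 5 is ordered and directional, the only test named outright for it is neither, and the alternative route would test order only under a specification that the plan does not give.

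Against a linear trend, for 3 to 6 levels, ANOVA gives up about 9 to 26 power points at 0.43 SD, 2 to 19 at 0.6 SD and under 5 at 0.8 SD. When the middle three of five levels are 0.4 SD better and the top equals the bottom, it rejects about 73% of the time, against 5% for the trend test with equal levels and 17% with the unequal sizes shown.

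These figures rest on 270 independent persons, two-sided 0.05 and assumed effects. They ignore clustering by building and the fact that participants largely choose their own dosage. The mismatch between hypothesis and test does not depend on any of these assumptions.

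**What to change.** In Section 12.4, make the predictor route the test of Hypothesis 5:

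- Fix the dosage levels and their scores in advance, and enter the score as a single numeric term (1 df) in the outcome model.
- Report the slope with its 95% CI. Count Hypothesis 5 as supported only if the slope is significant in the favourable direction, which is negative for the Gingival Index and Plaque Score.
- Show the level means, and keep the ANOVA or a departure-from-linearity test as a secondary check of shape, because a trend test alone does not rule out a non-monotone pattern.

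This takes a few lines of plan wording and no new data. The price is slightly lower power if the effect is a pure threshold (46% against 53% with five levels at 0.4 SD), a pattern that the retained shape check is there to reveal.

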The classical Barron & Kenny (1986) mediation approach to longitudinal mediation would examine whether the intervention impacts the levels of our mediators, such as beliefs, at T1 (for example), which in turn affect clinical outcome measures resulting from participant behaviors as measured by the Gingival index and Plaque Scores at T2. Or, simply put, whether levels of self-efficacy at T1 are associated with the levels of gingival index scores at T2 indirectly through self-efficacy at T1 (and other mediators previously referenced). But, we are interested in examining whether there is a change in our mediators over time, and if so, whether this change significantly leads to a change in behaviors, as assessed by the Gingival Index and Plaque Scores. Recent methodological studies actually show that the analysis of change is more appropriately captured by specifying change (differences) in self-efficacy and our other mediators and behavioral outcomes between adjacent time points (i.e. T1-T0, and T2-T1) as latent difference scores, and explicitly modeling these change scores to represent dynamic change, i.e., the impact of change in the mediators on change in the behavioral

Hypothesis #3 will be tested using latent change score analysis specifying AMI and Campaign as predictors of change in behavioral beliefs(ΔBB), OH social support (ΔSS), locus of control beliefs(ΔCB), self-efficacy(ΔSE), fears/worries ($\Delta F/W$), social norms (ΔSN), and behavioral intentions (ΔSI) from baseline to first and second follow-up.

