To test hypothesis #4, we will conduct dynamic mediation using latent change (difference) score (LCS) mediation analysis. The analyses will be conducted in Mplus 7 where change (difference) scores representing differences in each mediator and outcome variable from baseline to final follow up (i.e. T1-T0 (ΔT_{10}), and T2-T1(ΔT_{21}) will be generated. It is the difference scores of the mediators and outcome variables that are modeled. Generally speaking, causal paths specifying latent (true) change, represented by change in knowledge, oral health beliefs/norms, OH social support, oral hygiene behaviors, fears/worries, oral health practice to mastery skills, and behavioral intentions in going from T0 to T1, and T1 to T2 will be specified, to predict change in Gingival Index and Plaque Scores at T2 (i.e., ΔGingival Index₂₁, ΔPlaque score₂₁). For example, we will test whether change in fears/worries from T0 to T1 significantly predicts changes in Gingival Index and Plague Scores at final follow-up, T2 (ΔGingival Index₂₁, Δ Plague scores₂₁). To assess the impact of the change in self-efficacy (Δ SE). on changes in Gingival Index scores (ΔGingival Index), direct and indirect paths from change in self-efficacy from baseline to first follow up (ΔSE₁₀) that predict the change in Gingival Index at the final follow-up (ΔGingival Index₃₀) will be specified and tested. Select direct and indirect paths from change scores of the other mediator variables to change scores of behavioral outcomes will also be specified in a similar fashion, and all these relationships will be tested simultaneously.

Summary: Using a conservative set of assumptions and based on our own pilot data, we have demonstrated, using our pilot data estimates, that we will have sufficient power to detect significant changes, using a two-group t-test which makes minimal

IRB Review
IRB NUMBER: 14-188-6
IRB APPROVAL DATE: 01/03/2019
12/14/2018

Good Oral Health: A Bi-level Intervention to Improve Older Adult Oral Health Protocol #14-046-E

assumptions about the data. It is worth noting that the proposed statistical models have greater power characteristics than the t-tests used to calculate power.

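### The self-efficacy mediation path names a Gingival Index change (subscript 30, T0 to T3) that conflicts with the rest of Section 12.4 and overlaps the mediator's own interval

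*Combined protocol and SAP*

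**What the plan says.** All of this is in Section 12.4, Final Analysis Plan, in the text on latent change score mediation.

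- The principle is to model change in mediators and "behavioral outcomes between adjacent time points (i.e. T1-T0, and T2-T1) as latent difference scores".
- The scores to be produced are listed: "T1-T0 (ΔT_{10}), and T2-T1(ΔT_{21}) will be generated". Subscript jk therefore means Tj minus Tk. The same sentence presents these two scores as covering baseline to final follow-up, which makes T2 the final follow-up.
- The general statement has mediator change "in going from T0 to T1, and T1 to T2 will be specified, to predict change in Gingival Index and Plaque Scores at T2", and gives the outcomes as Gingival Index and Plaque Score change with subscript 21.
- The fears/worries example asks whether T0-T1 change "significantly predicts changes in Gingival Index and Plague Scores at final follow-up, T2", again with subscript 21.
- The self-efficacy example then commits to testing "direct and indirect paths from change in self-efficacy from baseline to first follow up" (subscript 10) "that predict the change in Gingival Index at the final follow-up", and here the outcome carries subscript 30.

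The remaining mediators are to be handled similarly, with all relationships tested together. No sentence explains why self-efficacy has a different outcome interval.

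**The concern.** Objective 3 asks whether change in cognitive and behavioral factors brings about clinical change, and Section 12.4 means to answer it by letting mediator change come before outcome change. A T0-T3 outcome starts at the same moment as the T0-T1 mediator change. Part of any association is then simultaneous: people whose gums improved between T0 and T1 may also have gained confidence in that interval, in either causal direction or through a common cause.

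The score can be computed, because Appendix A schedules a clinical assessment at T3. An analyst could run the path as printed and nothing would flag a problem. If the interval is left open, it will be chosen after the data are in. The degree of overlap also differs by sequence, and Section 12.4 uses this mediation analysis to compare the sequences.

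**Working it through.** **1. The statements side by side (Section 12.4)**

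| Statement | Mediator interval | Outcome interval |
|---|---|---|
| Scores to be generated | 10 and 21 | 10 and 21 |
| General statement | T0-T1 and T1-T2 | 21 |
| Fears/worries | T0-T1 | 21, at T2 |
| Self-efficacy | 10 | 30 |

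Subscript 30 is not among the generated scores, does not join adjacent time points, and moves the final follow-up from T2 to T3. The general statement also includes T1-T2 mediator change predicting T1-T2 outcome change, which is fully concurrent.

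**2. How much of the outcome window is shared**

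Inputs: T3 at 16-18 months after entry (Protocol Summary); the other timings from Appendix A.

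- Session first: session up to 45 days (1.5 months) after T0, then T1 1-3 months later. T1 falls at about 1 to 1.5 + 3 = 4.5 months. Shared part: 1/18 = 6% to 4.5/16 = 28%.
- Campaign first: campaign at 3-6 months, then T1 1-3 months later. T1 falls at about 4 to 9 months. Shared part: 4/18 = 22% to 9/16 = 56%.

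**3. What the overlap does**

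ΔGI30 = ΔGI10 + ΔGI21 + ΔGI32, so Cov(ΔSE10, ΔGI30) = Cov(ΔSE10, ΔGI10) + Cov(ΔSE10, ΔGI21) + Cov(ΔSE10, ΔGI32). The first term is purely concurrent.

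**4. Size under assumptions**

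The documents give neither the concurrent correlation nor the serial correlation of GI. Assume corr(ΔSE10, ΔGI10) = -r, no lagged effect of the mediator, N = 270 (Section 4), an unadjusted path, a two-sided 0.05 test, and no building clustering. The expected correlations are:

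- *Independent, equal-variance GI increments:* 30 path, -r/√3; 21 path, 0.
- *Stationary AR-1 levels with lag-1 correlation ρ, mediator change tied to ΔGI10 itself (form a):* 30 path, -r(1-ρ)(1+ρ²) / [2√((1-ρ)(1-ρ³))]; 21 path, +r(1-ρ)/2.
- *Same AR-1, mediator change tied only to the new GI disturbance since T0 (form b):* 30 path, -rρ²√((1-ρ)/(1-ρ³)); 21 path, +r(1-ρ).

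Example, r = 0.3 and ρ = 0.5. Form a: 0.3 × 0.625/(2 × 0.661) = 0.142 for the 30 path and 0.3 × 0.25 = 0.075 for 21. Form b: 0.3 × 0.25 × 0.756 = 0.057 and 0.3 × 0.5 = 0.150.

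Rejection rates at r = 0.3 (Fisher z approximation, within about 2 points of the simulations run):

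| GI model | 30 path | 21 path |
|---|---|---|
| Independent increments | 82% | 5% |
| AR-1, form a, ρ = 0.5 / 0.7 / 0.9 | 64 / 70 / 78% | 23 / 11 / 6% |
| AR-1, form b, ρ = 0.5 / 0.7 / 0.9 | 15 / 37 / 68% | 69 / 31 / 8% |

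The spurious 30 path always points toward benefit. The spurious 21 path, where present, has the opposite sign. Under independent increments the 30 path also moves with r: simulated rates are 15%, 45%, 82% and over 99% at r = 0.1, 0.2, 0.3 and 0.5.

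**5. What adjustment removes**

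Under AR-1, ΔGI21 = (ρ-1)GI1 + new disturbance. Conditioning on the T1 level of GI therefore removes the spurious 21 path in both forms (partial correlation 0). Conditioning on ΔGI10 alone removes it in form a but not fully in form b: at r = 0.3 and ρ = 0.5 the partial correlation is still 0.08.

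**The case against.** The strongest reply is that 30 is a slip. Several statements in the same text agree on 10, 21 and T2, and one subscript disagrees. That may well be right, but a slip in a sentence that says what will be tested still needs correcting, and the intended value is not self-evident. If 20 was meant, the interval still contains T0-T1: under independent increments the correlation is 0.3/√2 = 0.21, with about 94% rejection.

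Second, the plan does not test a single unadjusted path. It fits direct and indirect paths simultaneously. If ΔGI10 is a predictor in that model, the independent-increment result falls from 82% to about 5%. This stands as a limit on the size of the problem, because the text does not say whether earlier GI enters the model.

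Third, the 21 interval is not clean by construction. Section 12.4 itself expects an AR-1 structure for repeated clinical measures, and under AR-1 the unadjusted 21 path can reject more often than the 30 path. This also stands, and it is why changing the subscript is not enough.

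A reader might infer that every mediator is to be tested against T0-T3 change, or that the Objective 3 conclusion would rest on a concurrent correlation. The documents do not support either. Only self-efficacy and only the Gingival Index carry subscript 30. The general statement already assigns 21 to the mediators, and the remark that others follow similarly does not clearly override it. Objective 3 covers several mediators and two clinical outcomes.

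**Conclusion.** The inconsistency is certain from the text: the self-efficacy path uses a score that the plan does not otherwise generate, over an interval that breaks its adjacent-time-point rule. Taken literally, the path loses the time order that a mediation claim needs and can show a concurrent association as apparent benefit.

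The size is not determined by the documents. At an assumed concurrent correlation of 0.3, unadjusted rejection with no lagged effect runs from about 15% to 82%, and the ranking of the 30 and 21 intervals can reverse with the GI covariance. These figures rest on a simplified two-variable path that ignores clustering, and they show direction and range only.

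The treatment comparisons in Hypotheses 1 and 2 are unaffected. This is a minor point worth correcting because it changes which analysis is run.

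**What to change.** In Section 12.4:

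1. Replace subscript 30 with 21 on the self-efficacy path.
2. Replace each mention of the final follow-up with T2 or T3 by name.
3. State that the lagged paths (T0-T1 mediator change to T1-T2 outcome change) carry the mediation claim. Label the T1-T2 mediator to T1-T2 outcome paths as concurrent.
4. Include earlier Gingival Index or Plaque Score as a predictor of later change in the latent change model. The T1 level is the safer choice. If ΔGI10 is used, add the baseline level as well.
5. If a T3 outcome is wanted, use change starting at T1 or T2, as a labelled additional analysis with the same adjustment.

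The cost is a revised paragraph and a few extra model paths. Every measurement needed is already scheduled, so visits, data collection and sample size do not change.

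### The closing claim that the analysis models have more power than the sizing t-test is unsupported: the power table never reduces the degrees of freedom for three randomised buildings per condition

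*Combined protocol and SAP*

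**What the plan says.** Section 12.2 sizes the trial on the first period, which it calls "essentially a two-arm parallel design with randomization at the building level". The table is headed "Sample size for a two-group t-test, using a two-sided α =0.05", and its least favourable row reads "Plaque Index Pilot*.75 0.20 0.47 (UCL) 0.42 123 91". On clustering, the section says "With this design we expect to have 6 clusters of N=45 each finish the study, or 135 per sequence". It then lowers the number per group from 135 to 123 for an intracluster correlation (ICC) of 0.01 or 0.02 and reports: "Using N=123 per group, our power ranged from 91 to 99 for different scenarios reflecting varied assumptions".

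Section 5 assigns one building of each matched pair to each condition, and section 5.4.1 says that individuals are not randomised.

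The analysis text in section 12.4 plans standard two-arm methods for period 1 and a repeated-measures model, clustered on the person, for periods 1 and 2. It names no building term, pair term or small-sample df correction. The Summary then says there is "sufficient power to detect significant changes, using a two-group t-test which makes minimal" assumptions, and adds that "the proposed statistical models have greater power characteristics than the t-tests used to calculate power".

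**The concern.** The closing sentence invites the reader to treat the tabulated 91 to 99% as a floor. In a trial that randomises six buildings, the comparison of conditions rests on variation between buildings. A test that respects this has 6 − 2 = 4 df, or 3 − 1 = 2 df if the pairs are kept. The sizing t-test has 2 × 123 − 2 = 244.

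Reducing n for the ICC corrects the standard error. It does not correct the critical value, which is 1.97 on 244 df, 2.78 on 4 df and 4.30 on 2 df. Power for plaque, one of two primary outcomes, may therefore be well below what is stated, and below the 80% that section 12.2 mentions as its target.

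**Working it through.** **Inputs (section 12.2 unless noted).** Two-sided α 0.05; n = 123 per group; conservative plaque difference 0.20 with SD 0.47; conservative gingival difference 0.50 with SD 0.81; three buildings per condition; 45 completers per building; ICC 0.01 or 0.02. Pilot SDs (section 2.1): plaque 11.8% then 31.2%; gingival 0.56 then 0.47.

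**Formula.** Noncentrality = (difference/SD) × √(n/2), with √(123/2) = 7.842. Power is the noncentral-t probability beyond ± the critical value.

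**Step 1: reproduce the plan.** Plaque: 0.4255 × 7.842 = 3.34, which on 244 df gives 91.4% (stated 91). Gingival: 0.6173 × 7.842 = 4.84, which gives 99.8% (stated 99). The plan's figures come from individual-level df.

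**Step 2: change only the df, keeping n = 123.**

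| Row (difference/SD) | Stated | 244 df | 4 df | 2 df |
|---|---|---|---|---|
| Plaque 0.25/0.34 | 99 | >99.9% | 98.6% | 81.2% |
| Plaque 0.25/0.47 | 98 | 98.6% | 87.0% | 59.3% |
| Plaque 0.20/0.47 | 91 | 91.4% | 70.7% | 44.8% |
| Gingival 0.66/0.81 | 99 | >99.9% | 99.6% | 87.0% |
| Gingival 0.50/0.81 | 99 | 99.8% | 94.4% | 69.7% |

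The loss does not depend on how 123 was obtained. With n = 135 and no ICC loss, conservative plaque is 93.6%, 74.4% and 47.6% on individual-level, 4 and 2 df.

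**Step 3: what baseline adjustment would have to do.** Reaching 91.4% on 4 df needs a noncentrality of 4.52. The variance must fall to (3.34/4.52)² ≈ 0.546 of its value, so the T0 correlation must be √(1 − 0.546) ≈ 0.67. If 0.47 is the SD of a follow-up value, a correlation of 0.5 gives 82%, 0.6 gives 87% and 0.7 gives 93%.

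**Step 4: what the pilot suggests, assuming the tabulated 0.34 and 0.60 are SDs of change.**
- Plaque correlation: (0.118² + 0.312² − 0.34²)/(2 × 0.118 × 0.312) ≈ −0.06. Residual SD: 0.312 × √(1 − 0.06²) ≈ 0.3115, a ratio of 0.3115/0.34 = 0.916. Applied to 0.47, this gives 0.431, noncentrality 3.64, and 78% on 4 df.
- Gingival correlation: (0.56² + 0.47² − 0.60²)/(2 × 0.56 × 0.47) ≈ 0.33. Residual SD: 0.47 × √(1 − 0.33²) ≈ 0.443, a ratio of 0.739. Applied to 0.81, this gives 0.599, noncentrality 6.55, and 99.7% on 4 df.

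**Step 5: the effective n that the stated ICC implies.** The design effect is 1 + 44 × 0.01 = 1.44, or 1 + 44 × 0.02 = 1.88. Effective n per arm is 135/1.44 = 93.8, or 135/1.88 = 71.8. An effective n of 123 corresponds to an ICC of (135/123 − 1)/44 ≈ 0.002. On 4 df without baseline adjustment:

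| ICC | Effective n | Conservative plaque | Conservative gingival |
|---|---|---|---|
| 0.01 | 94 | 59.5% | 87.8% |
| 0.02 | 72 | 49.2% | 78.8% |

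**The case against.** The strongest reply is that repeated-measures and covariate-adjusted models do gain precision, and section 12.4 provides for both. This stands in part. A reader might infer that the t-test figures are a ceiling; the documents do not support that. A high enough baseline correlation brings plaque back to 91% on 4 df or beyond, and under the SD-of-change assumption the adjusted gingival model essentially matches the sizing t-test (99.7% against 99.8%). Section 12.4 also lists covariates whose value cannot be quantified here. But the plan gives no correlation, and the pilot-based plaque value comes from 30 people and an assumed meaning of 0.34.

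A second reply is that a model clustered only on the person would show higher nominal power. It would, by ignoring the randomised unit. An individual-level test taking no account of buildings would have a true error rate of about 2 × [1 − Φ(1.96/√1.44)] ≈ 10% at ICC 0.01, or 2 × [1 − Φ(1.96/√1.88)] ≈ 15% at 0.02. That is not usable power.

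Third, the plan does allow for clustering through n, so it is too strong to say that it treats residents as simply independent. What is missing is the df. The remark about minimal assumptions can be read as needing few modelling inputs, and removing it is a matter of wording.

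Fourth, the sentence fixes no sample size, test or decision rule, and nothing in the documents says that a null plaque result would be read as showing no difference. Both are true. The sentence is still a stated power property without support.

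**Conclusion.** The claim of greater power is unsupported, and the tabulated plaque power is not delivered by a test that respects six randomised buildings. At the plan's own n = 123, conservative plaque power is about 71% on 4 df against 91 stated, and conservative gingival power about 94% against 99. The 2-df figures, 45% and 70%, apply only if the pairs are kept in the analysis, which section 12.4 does not specify.

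A reader might infer that both primary outcomes are underpowered. On 4 df at n = 123 the gingival rows stay at 94% or more, so that does not follow from the df alone. Nor are 71% and 94% final figures: they keep an n that the stated ICC does not support.

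The result rests on the table's differences and SDs, equal building sizes and no baseline adjustment. With adjustment, under the SD-of-change assumption, plaque is about 78% and gingival about 99.7% on 4 df at n = 123.

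**What to change.** - Delete the sentence on greater power from the Summary in section 12.4. Removing the minimal-assumptions remark is optional.
- Restate the section 12.2 table and the Summary for a building-level test, showing its df: 4, or 2 if the pairs are retained. Say which analysis is intended.
- In the same revision, use an effective n that follows from the stated ICC: 94 or 72 per arm at 45 per building. Before baseline adjustment, on 4 df, this gives about 60% or 49% for conservative plaque and 88% or 79% for conservative gingival.
- Correct the reduced plaque difference as well: 0.75 × 0.25 is 0.1875, not 0.20. At n = 123 this alone gives 87.6% on 244 df and 65.4% on 4 df.
- If baseline adjustment is relied on, state the assumed correlation for each outcome and its source.

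The cost is some wording and one recalculated table. No extra participants are needed; the stated power becomes less favourable.
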